- **Enrollment:** After consenting to the study, participants will receive the initial survey via text web-link or email link. **Survey 1** asks questions about the participant's hypertension history, experience with prenatal care and care at delivery, and socio-demographic questions not reliably obtained from the electronic health record. We estimate that this survey will take 15 minutes to complete. Participants will receive a \$10 gift card for completion.
- **Randomization and Procedures before Hospital Discharge:** All participants will receive an Omron [validated blood pressure monitor](#) with appropriately sized cuff (Appendix A) following measurement of their arm circumference. Many of our patients do not obtain blood pressure cuffs postpartum, and they infrequently are covered by insurance providers. Instructions for blood pressure measurements and discharge instructions will be discussed with the patient and sent via MyHealth messaging with the script described in Appendix B. Participants will be instructed to measure blood pressure after being seated for 10 minutes with legs uncrossed and back supported with their arm positioned at the level of their heart. They will be instructed to avoid caffeine and tobacco for 30 minutes prior to measuring blood pressure. If blood pressures reach a predefined target threshold (Interventions C and D), they should wait 15 minutes and repeat the blood pressure measurement. Participants will be instructed to bring their blood pressure cuff to their first follow up appointment for calibration and clinical correlation. At hospital discharge, participants will receive information regarding follow up after HDP: a) seeking care for sustained severe blood pressures ($\geq 160/110$ mmHg at least 15 minutes apart), b) preeclampsia alert symptoms (headache, confusion, or visual changes), and c) scheduling an appointment with a primary care clinician at 3 months postpartum. All patients will receive a written letter explaining the study (Appendix C) that they can take to clinician visits outside the VUMC system. At discharge, a follow up in-person visit for a blood pressure check within 7-10 days postpartum will be requested by the inpatient team, which is our routine practice. Our specific research interventions are:

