Aim 1 Analytic Approach: Our primary analysis will examine the independent effect of the interventions (blood pressure goals and monitoring approach) on the primary outcomes. While randomized trials greatly reduce confounding, they do not eliminate it, and covariate adjustment enhances statistical power. Balance in participant's demographic and clinical characteristics across the four groups (control + 3 interventions) will be compared using the Mann-Whitney *U* test for continuous variables and Chi squared test for categorical variables. Characteristics that exhibit differences across groups and potential confounding variables such as race, socioeconomic status, and medical comorbidities will be considered as adjusting covariates in the subsequent regression analysis. Multiple linear regression with ordinary least square estimates (OLS) will be used to compare the SBP and DBP primary outcomes across four interventions with a binary variable for the monitoring intervention (standard vs augmented), a binary variable for the blood pressure goal intervention (standard 150/100 and tight 140/90) and an interaction term between the two binary variables for the combined interventions. A negative value for two main effects of interventions indicates better blood pressure control using individual interventions alone than the standard of care. A negative value for the interaction effect indicates better blood pressure control using combined intervention than individual intervention alone. Post hoc analysis of variance (ANOVA) can be conducted to assess the overall effect of each individual interventions (with 2 degree of freedom) and the overall intervention effects (with 3 degree of freedom). Although OLS does not require normality assumption for outcomes and residuals, extreme outliers might result in potential bias. In this case, a non-parametric model (e.g. proportional odds model) will be considered. This analysis will be repeated allowing the primary outcome to include mean blood pressures reported via augmented remote monitoring among women who do not attend in-office visits. Multiple logistic regression will be conducted for binary outcomes including the severe hypertension primary outcome, hypertension secondary outcomes and healthcare utilization secondary outcomes. The same main effects and interaction effects for interventions specified for the linear regression model will be included with negative values for the log-odds ratio indicating improved outcomes in the intervention groups. Linear regression with OLS will be used for patient-reported secondary outcome measures in a similar fashion as SBP and DBP primary outcomes. Given the prospective design and dedicated personnel, we anticipate little missing covariate data. In case there are more than 1% participants with missing data in the analysis, multiple imputation will be conducted as sensitivity analysis. All outcomes will be analyzed as intent-to-treat.

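### No primary method is given for missing covariates, so by default the adjusted primary models leave out women whose outcome was observed

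*Combined protocol and SAP*

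**What the plan says.** All references are to the combined protocol and SAP.

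- **Models** (ANALYTIC APPROACH, Aim 1): "Multiple linear regression with ordinary least square estimates (OLS) will be used to compare the SBP and DBP primary outcomes". Logistic regression is used for binary outcomes, including severe hypertension.
- **Covariates** (same section): characteristics that differ between groups and "potential confounding variables such as race, socioeconomic status, and medical comorbidities will be considered as adjusting covariates in the subsequent regression analysis". No fixed list is given.
- **Missing data** (same section): "Given the prospective design and dedicated personnel, we anticipate little missing covariate data". Then: "In case there are more than 1% participants with missing data in the analysis, multiple imputation will be conducted as sensitivity analysis". Aim 2 handles missing data in a similar way.
- **Analysis principle** (same section): "All outcomes will be analyzed as intent-to-treat". The term is not defined.
- **Source of the covariates** (STUDY PROCEDURES, Enrollment): "After consenting to the study, participants will receive the initial survey via text web-link or email link". Among other things, this survey asks "socio-demographic questions not reliably obtained from the electronic health record".

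**The concern.** Multiple imputation is reserved for a sensitivity analysis and nothing else is offered. The primary models therefore have no stated way to keep a woman whose covariates are incomplete. Ordinary least squares and logistic regression, fitted without such a method, omit the whole record.

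The reasons given for expecting few gaps are prospective design and dedicated staff. They fit poorly with items that the participant enters herself, and for which the protocol calls the health record unreliable. A woman with an in-office blood pressure or a recorded readmission could leave the primary model because one survey item is blank.

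Three things are at stake:

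- The primary result could rest on women with complete surveys instead of all randomised women with an outcome.
- Because balance tests help decide which covariates enter, the analysed set is not known in advance.
- Aim 2 compares Black and non-Black women within standard care. That contrast is not randomised, so non-response related to race could distort it directly.

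**Working it through.** **Inputs.** From Power and Sample Size Considerations and Table 6: alpha 0.05 (taken as two-sided, since the plan does not say), 80% power, 250 v 500 women, 0.22 SD. From Table 5: 1053 women retained to 6 weeks. The share *m* of women with at least one missing adjusted covariate is **not in the documents**. I assume 1%, 5%, 10% and 20%, lost at random and equally across groups.

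**Formulas** (normal approximation), with n1 in standard care and n2 = 2·n1:

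- Detectable difference = (1.960 + 0.842) × √(1/n1 + 1/n2)
- Power at 0.22 SD = Φ(0.22 / √(1/n1 + 1/n2) − 1.960)

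**Plan's figure reproduced.** 2.8016 × √(1/250 + 1/500) = 0.217, which rounds to the stated 0.22. Power at 0.22 SD = Φ(0.22 × 12.910 − 1.960) = Φ(0.880) = 81.1%.

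**With loss.** Put n1 = 250(1 − m) for the powered 1000 women, or n1 = 1053(1 − m)/4 for the projected retained sample.

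| m (assumed) | Women omitted of 1000 | Groups | Detectable difference (SD) | Power, from 1000 | Power, from 1053 |
|---|---|---|---|---|---|
| 0 | 0 | 250 v 500 | 0.217 | 81.1% | 83% |
| 1% | 10 | 247.5 v 495 | 0.218 | 80.7% | 83% |
| 5% | 50 | 237.5 v 475 | 0.223 | 79.1% | 81% |
| 10% | 100 | 225 v 450 | 0.229 | 76.9% | 79% |
| 20% | 200 | 200 v 400 | 0.243 | 71.9% | 74% |

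Example at 10%: Φ(0.22 × √150 − 1.960) = Φ(0.734) = 76.9%.

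For severe hypertension (10.2% reduced by 57%, no continuity correction), power goes from 84.1% with no loss to 80.5% at 10% and 76.1% at 20%.

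**Gain from adjustment.** The plan's power figures ignore covariates. If the covariates explain a share R² of the outcome variance, the effective sample is multiplied by (1 − m)/(1 − R²). With m = R² = 10%, the factor is 0.90/0.90 = 1 and power returns to 81.1%. R² is not in the documents, so the net effect cannot be signed.

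**The case against.** The case against has several sound parts.

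- **Silence is not a rule.** A reader might infer that the plan drops every woman with a missing covariate. It never says so. Complete case is the default implied by the absence of another primary method. The covariates are only to be considered, so loss occurs only if incomplete items enter the model.
- **Exposure is narrower than it looks.** Race is a stratification factor and should be known for every randomised woman. No section says that comorbidities come from Survey 1, although it does ask about hypertension history. Socioeconomic status is the clearest case.
- **Completion may be good.** Women unable or unwilling to receive electronic surveys are excluded. Recruitment is at the bedside, and Survey 1 carries a gift card and is listed before the randomisation step. Nothing makes randomisation wait for it, but nothing shows completion after allocation either.
- **Intent-to-treat.** A reader might infer a contradiction. The term is undefined, and in its minimal sense of analysis as randomised it is not breached. The tension is with including all randomised women.
- **Omitted women need not all have outcomes.** The SBP and DBP outcomes are in-office readings at 7-10 days, which non-attenders lack, and women who skip the survey may also be those who miss visits. The counts in the table are therefore upper bounds on observed blood pressures lost.
- **Power.** The 1053 projected in Table 5 absorbs about 5% loss (1053 × 0.95 = 1000), and adjustment may recover more. At the plan's own 1% trigger the cost is 0.4 points.

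What remains is that the primary handling is unstated, the likely default discards usable outcomes, and a better method costs almost nothing. The 1% trigger would expose a discrepancy but would not change the primary result.

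**Conclusion.** The concern holds in this limited form: the plan gives no primary method for missing covariates, and the implied default leaves out women with observed outcomes. The self-completed survey means the loss could exceed what the plan expects, but the documents do not show that it will. At 1% it is trivial. At 10% power is about 77% on 1000 women or 79% on 1053, and at 20% it is 72% or 74%. These figures assume two-sided 0.05, the plan's own 250 v 500 comparison, loss at random and no gain from adjustment.

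The stronger argument is an undetermined analysis set with possible selection, above all in Aim 2's race contrast; power comes second. Missing outcomes (25% not retained to 6 weeks, and in-office readings only) are a separate and possibly larger problem that this point does not settle.

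**What to change.** In the Aim 1 Analytic Approach, replace the missing-data sentence with the following:

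1. The primary models include every randomised woman whose outcome is observed.
2. For the randomised comparisons, missing baseline covariates are filled without using arm or outcome: the overall mean for continuous covariates and a separate category for missing categorical values.
3. Complete-case analysis becomes the sensitivity analysis.

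Fix the covariate list in advance, so that the rule applies to known variables. Simple filling relies on the gaps not being caused by allocation, so report how many women completed Survey 1 after allocation.

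In the Aim 2 Analytic Approach, use multiple imputation as the primary method for the Black/non-Black contrast within standard care, and specify its model. That contrast is not randomised, and mean or missing-category filling can leave confounding in it.

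The cost is SAP wording and a few lines of code, with no new data. A rule for missing outcomes has to be written separately.

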We propose a comprehensive management program for postpartum patients with HDP who are at risk for severe maternal morbidity and mortality. Our program will emphasize three key components: 1) self-monitoring of blood pressures with app-based reporting connected to our electronic health record, 2) blood pressure management directed by a program navigator with guideline and physician support and 3) facilitated transitions of care to primary care clinicians for hypertension management. We will randomize 1400 patients with HDP on postpartum day one with follow up through 3 months postpartum. Primary outcome will be blood pressure control at 2 weeks postpartum. Secondary outcomes include identification and treatment of severe blood pressures, severe maternal morbidity, postpartum and primary care visit attendance, and multiple patient-reported outcome measures. All outcomes will be stratified by race (Black and non-Black) to evaluate disparities and by tight versus usual blood pressure control to evaluate the impact of strict postpartum blood pressure control on outcomes. We hypothesize that a comprehensive postpartum HDP management program will improve hypertension control for all patients and reduce disparities that affect Black patients, and that stricter blood pressure control will be associated with fewer adverse outcomes.

OBJECTIVE

Specific Aim 1: To assess whether augmented remote blood pressure monitoring and tight blood pressure control, both individually and in combination, improve blood pressure control and the frequency of severe hypertension in the first 2 weeks postpartum.

Specific Aim 2: To test whether these interventions narrow the existing Black/non-Black inequity in postpartum outcomes such as blood pressure control and severe hypertension.

ELIGIBILITY CRITERIA

Inclusion Criteria

1. Age ≥ 18 years
2. Diagnosed with a Hypertensive Disorder of Pregnancy (HDP), which includes chronic hypertension, preeclampsia, gestational hypertension, HELLP Syndrome (Hemolysis, Elevated Liver enzymes, Low Platelets), or eclampsia (O10, O11, O13, O14, O15, O16)

Exclusion Criteria

1. Not able or willing to receive electronic surveys
2. Deemed inappropriate for study enrollment by bedside nurse
3. Non-English speaking
4. Discharge on postpartum day 6 or greater
5. Contraindication to ACOG-recommended hypertension control (i.e. chronic kidney disease, stroke)

SCREENING

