
Specific Aim 2: To test whether these interventions narrow the existing Black/non-Black inequity in postpartum outcomes such as blood pressure control and severe hypertension.

Aim 2 Analytic Approach: Given racial disparities in postpartum outcomes and hypothesized heterogeneity of intervention effect, we plan for two pre-specified subgroup analysis in (1) standard care only (N=250) (2) Black participants only (N=500). The first subgroup analysis aims to assess racial disparities in postpartum outcomes without intervention where Black/non-Black will be the main effect of interests. The second subgroup analysis aims to reassess intervention effects observed in Aim 1 but within Black participants. To test the hypothesis of the interventions narrowing racial inequity,

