we will use the overall cohort (N=1000) and additionally include the interaction between Black/Non-Black and the intervention effects (two main effects + one interaction effects) on top of all models in Aim 1. Missing data will be handled in the similar fashion as Aim 1. **Power and Sample Size Considerations (All Aims):** For Aim 1, power consideration is conducted in the setting of two group comparisons with sample size of N=250 (N=75 for Aim 3) in the standard care group and N=500 (N=150 for Aim 3) for each individual intervention instead of in the setting of 2x2 factorial design with N=1000 (N=300 for Aim 3) because the effect size of F-statistics for continuous outcomes and chi-square statistics for binary outcomes is not clinically interpretable. Review of institutional data found that 10.2% of patients with HDP at delivery experience sustained severe hypertension within the first 6 weeks postpartum and these patients have a mean SBP of 138 (SD 17.2) and mean DBP of 83 (SD 11.9). We will have 80% power to detect a minimum of 0.22 standardized reduction in SBP and DBP (a small effect by Cohen's nomenclature¹⁰³) which corresponds to reduction in SBP from 138 to 134 mmHg and DBP from 83 to 80 mmHg. Additionally, we will have 80% power to detect 57% reduction in sustained severe hypertension. Minimum detectable effect sizes for selected secondary outcomes in Aim 1 and the primary outcome for Aim 3 are provided (Table 6). For Aim 3, we will have 80% power to detect a minimum of 0.4 standardized difference in cardiovascular outcomes (a medium effect by Cohen's nomenclature), which corresponds to an increase of lateral e' from 11.7 to 13.1. For Aim 2, power justification is conducted based on N=300 using analysis of variance (ANOVA) for the interaction terms between race and interventions effects (with 3 degree of freedom) for the SBP and DBP primary outcomes. The minimum detectable F-statistics for the overall interaction term is 0.19 which is small-to-medium effect by Cohen's nomenclature. The power consideration does not consider adjusting covariates and thus is conservative since inclusion of adjusting covariates will improve the power of the study.

Table 6: Minimum detectable Relative Risk (alpha=0.05, 80% power, N=1000)

Outcome	Baseline	Minimum Detectable RR or Effect Size
Mean systolic blood pressure (SD)	138 (17.2)	4
Mean diastolic blood pressure (SD)	83 (11.9)	3
Sustained severe blood pressure (%)	10%	43%
Postpartum visit attendance (%)	40%	63%

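### Aim 2 adds race-by-intervention terms to every Aim 1 model without saying which outcomes and which test decide, and without multiplicity control

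*Combined protocol and SAP*

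**What the plan says.** The objective of Aim 2 is to test whether the interventions "narrow the existing Black/non-Black inequity in postpartum outcomes such as blood pressure control and severe hypertension". Blood pressure control and severe hypertension appear there only as examples.

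The Aim 2 Analytic Approach plans two subgroup analyses. One is in the standard-care arm. The other is in Black participants, and its purpose is given as follows: "The second subgroup analysis aims to reassess intervention effects observed in Aim 1 but within Black participants". The test of narrowing comes separately: "we will use the overall cohort (N=1000) and additionally include the interaction between Black/Non-Black and the intervention effects", with the scope given as "two main effects + one interaction effects) on top of all models in Aim 1". The Aim 1 Analytic Approach defines those models as linear regression for SBP and DBP, logistic regression for severe hypertension and the other binary hypertension and utilization outcomes, and linear regression for the patient-reported outcomes. The opening summary is equally broad: "All outcomes will be stratified by race (Black and non-Black) to evaluate disparities".

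The power section describes the Aim 2 calculation as an ANOVA "for the interaction terms between race and interventions effects (with 3 degree of freedom) for the SBP and DBP primary outcomes", based on N=300, with a minimum detectable value of 0.19. The only alpha given is 0.05, in the title of Table 6. For Aim 2 the plan gives no deciding outcome or term, no testing order, no alpha split and no exploratory label.

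**The concern.** Aim 2 is worded as a hypothesis test and is one of the trial's two stated aims. Its outcome list is open, and each model carries three race-by-intervention terms: race by monitoring, race by goal, and race by their interaction. Nothing says whether the three are judged together or one at a time. An analyst who follows the text could base a statement that the gap narrowed on any outcome, and on any of its terms, that falls below 0.05.

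The word primary does not settle the question. The Outcomes section first gives the primary outcome as having a blood pressure recorded in the office at 7–10 days. It then gives mean SBP, mean DBP and sustained severe hypertension as co-primaries. At stake is the error rate behind the trial's equity conclusion.

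**Working it through.** **The plan's own figure.** Noncentral F with numerator df 3, 8 cells (race × monitoring × goal), denominator df 300 − 8 = 292, noncentrality f² × N, alpha 0.05. The minimum f at 80% power is 0.192, and power at f = 0.19 is 79.1%. The stated 0.19 therefore reproduces at N=300 as Cohen's f for one unadjusted 3-df test. At the N=1000 used in the analysis text, the same calculation gives 0.105.

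**Inputs for the error rates**
- Outcomes, from Table 3: 5 hypertension (3 marked primary) + 5 utilization + 8 patient-reported = 18. The repeat SBP and DBP models that add remote readings are not counted.
- Cell size: N=1000, 1:1:1:1 allocation, half Black by target, so 1000 / 4 / 2 = 125.
- Alpha 0.05 per test. This comes from Table 6, is taken as two-sided, and is assumed to apply to Aim 2.
- Between-outcome correlation: not in the documents. Assumed 0 to 0.8, equal for all pairs.
- Truth: no race interaction on any outcome.

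**Independent case, one 3-df test per outcome.** The chance of at least one significant result over k outcomes is 1 − 0.95^k.
- k = 2: 1 − 0.9025 = 9.8%
- k = 3: 1 − 0.8574 = 14.3%
- k = 18: 1 − 0.3972 = 60.3%

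**Correlated case.** Simulation of the eight-cell model with the plan's dummy coding and a normal approximation for all outcomes (40,000 replicates). The 3-df cut-off is chi-square 7.815. A term counts as narrowing if z < −1.96. In each cell the first figure is at correlation 0.8 and the second at 0.

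| Outcomes counted | 3-df test, either direction | Any single term in the narrowing direction | 3-df test and a narrowing term |
|---|---|---|---|
| SBP, DBP | 8–10% | 11–14% | 4–5% |
| Three co-primaries | 10–14% | 14–20% | 5–7% |
| All 18 | 23–60% | 29–73% | 13–37% |

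At correlation 0.5, the 18-outcome row reads 41%, 51% and 24%. For one outcome, the chance that at least one of the three terms is significant in the narrowing direction is already about 7%.

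**After a correction.** The strictest Holm step over three tests is 0.05 / 3 = 0.0167. With every 3-df test held to that level, the simulated family-wise rate over three outcomes is 4.6% to 4.9% (correlation 0.5 and 0). The minimum f at N=1000 is 0.105 unadjusted, 0.114 at alpha 0.025 and 0.119 at 0.0167. At N=300, power at f = 0.19 would fall from 79% to 65% at 0.0167.

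**The case against.** The best defence is that the plan is narrower than its analysis sentence suggests. The power section ties Aim 2 to one overall 3-df interaction test on SBP and DBP. Table 3 separates primary from secondary outcomes, and the two examples in the aim match the three co-primaries. If those outcomes decide, and a claim of narrowing needs both a significant 3-df test and a term in the right direction, the error is 4–7%, which is close to nominal. The larger figures count every secondary outcome as an equal route to the claim. They also rest on an assumed correlation, and the 3-df figures count a widened gap as well as a narrowed one. Finally, no alpha is stated for Aim 2, so testing each term at 0.05 is an inference from Table 6 and from silence on adjustment.

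Most of this stands as a limit on size. It does not remove the gap. A power statement is not a decision rule, and the analysis text in the same section extends the terms to all Aim 1 models. The power text also omits severe hypertension, which the aim names. Even on the narrowest reading, two unadjusted 3-df tests carry 8–10% rather than 5% for a claim that the effects differ by race. The reading that keeps the error near nominal is reasonable, but the plan does not require it.

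**Conclusion.** The point holds as an unspecified decision rule with inflated error. The inflation is modest if only the primary outcomes decide and large if any Table 3 outcome may. The size depends on the assumed correlation, equal cells of 125, a two-sided 0.05 per test and a normal approximation for the binary outcomes.

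Two stronger readings are tempting, and the documents support neither.

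- A reader might infer that a false narrowing claim is more likely than not. That needs all 18 outcomes to count. It also needs either single terms read separately with correlation up to about 0.5, or any 3-df result in either direction with correlation up to about 0.3. The plan fixes neither the form of the test nor the correlation.
- A reader might infer that the Black-only re-analysis adds false narrowing claims, or will hide a real benefit. The plan keeps that analysis apart from the narrowing test, which uses the full cohort. With a 0.22 SD effect equal in both groups, power is about 94% for 500 v 500 (0.22 × √250 = 3.48; 3.48 − 1.96 = 1.52) and 69% for 250 v 250 (0.22 × √125 = 2.46; 2.46 − 1.96 = 0.50). That is the ordinary loss in a half-size subgroup, and nothing in the plan treats non-significance there as absence of benefit.

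**What to change.** In the Aim 2 Analytic Approach:

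1. Name SBP and DBP at 7–10 days and sustained severe hypertension by 6 weeks as the only confirmatory Aim 2 outcomes. They match the aim's own wording and the co-primaries in Table 3.
2. Make the single 3-df race-by-intervention test the deciding test for each: the F test for SBP and DBP, and its logistic counterpart for severe hypertension. Apply Holm across the three tests (0.0167, 0.025, 0.05), not across the individual terms.
3. Claim narrowing only when that test is significant and the estimated gap is smaller under intervention. A 3-df test has no direction, so state in advance which contrast with standard care measures the gap.
4. Label race interactions on all other outcomes as exploratory.
5. Report effects in Black and non-Black women side by side with 95% CIs from the full-cohort interaction model.

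The change is to SAP wording only. The cost is fewer confirmatory claims and slightly lower power per test: minimum f at N=1000 goes from 0.105 to about 0.119 at the strictest step. That figure assumes N=1000, so the N=300 in the Aim 2 power text should be reconciled with the analysis N. The power text covers SBP and DBP only, so the SAP should also state the power for the race interaction on severe hypertension.

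### Aim 1's 80% power is calculated for 250 v 500, a comparison no planned analysis makes; at 0.22 SD the described model has about 69% (250 v 250) and the factorial margin about 94% (500 v 500)

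*Combined protocol and SAP*

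**What the plan says.** Under 'Power and Sample Size Considerations (All Aims)', Aim 1 is powered as a two-group comparison with "N=250 (N=75 for Aim 3) in the standard care group and N=500 (N=150 for Aim 3) for each individual intervention". The section says openly that this replaces the 2x2 factorial setting with N=1000, because effect sizes for F and chi-square statistics are hard to read clinically. It then states: "We will have 80% power to detect a minimum of 0.22 standardized reduction in SBP and DBP", given as 4 mmHg systolic and 3 mmHg diastolic. For the third co-primary outcome, "we will have 80% power to detect 57% reduction in sustained severe hypertension". Table 6 repeats these figures at alpha 0.05 and N=1000.

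'Aim 1 Analytic Approach' describes the analysis. It opens: "Our primary analysis will examine the independent effect of the interventions". The model has one binary variable for monitoring, one for the blood pressure goal, and "an interaction term between the two binary variables for the combined interventions". The coefficients are interpreted as follows: "A negative value for two main effects of interventions indicates better blood pressure control using individual interventions alone than the standard of care". Joint tests are optional: "Post hoc analysis of variance (ANOVA) can be conducted to assess the overall effect of each individual interventions (with 2 degree of freedom"), plus a 3-df test of all intervention effects.

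Allocation is 1:1:1:1 (Interventions, Table 1), so N=1000 means 250 per cell.

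**The concern.** A group of 500 for one intervention can be formed only by adding the 250 who receive both interventions to the 250 who receive that one alone. Comparing those 500 with the 250 on standard care estimates, if effects are additive, the intervention's own effect plus half of the other's. Nothing in the Aim 1 analysis does this.

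The analysis text supports two readings. The explicit interpretation of the main effects, in a model that keeps the product term, gives a 250 v 250 contrast. The opening sentence about the independent effect of each intervention could mean the 500 v 500 margin. The plan does not say which is primary, and the stated 80% belongs to neither.

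A null result therefore could not be judged against a known detectable effect. With the contrast left open, it could also be chosen after the data are seen.

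**Working it through.** **Inputs.** Alpha 0.05, 80% power, SD 17.2 (systolic) and 11.9 (diastolic), 10.2% sustained severe hypertension, and a 57% reduction (RR 0.43, so 10.2% to 4.39%), all from the power section and Table 6. Cells of 250 follow from 1:1:1:1 allocation at N=1000. Sidedness is not stated; two-sided is assumed because it reproduces the plan's figure (one-sided gives 88% for 250 v 500).

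**Blood pressure.** In SD units, SE = √(1/n₁ + 1/n₂). Power comes from the noncentral t distribution with noncentrality d/SE. The minimum detectable effect (MDE) is about (1.96 + 0.84) × SE.

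| Contrast | SE | Power at 0.22 SD | at 4/17.2 | at 3/11.9 | MDE |
|---|---|---|---|---|---|
| 250 v 500 (as powered) | 0.0775 | 81.0% | 85.0% | 90.2% | 0.217 SD |
| 250 v 250 | 0.0894 | 69.0% | 73.7% | 80.3% | 0.251 SD (4.3, 3.0 mmHg) |
| 500 v 500 | 0.0632 | 93.5% | 95.7% | 97.8% | 0.177 SD (3.1, 2.1 mmHg) |

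The first row reproduces the plan. The mmHg columns show higher power because 0.22 × 17.2 = 3.78 and 0.22 × 11.9 = 2.62 were rounded up to 4 and 3.

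**Which row the model gives.** The SEs can be taken from the design matrix with 250 per cell. With 0/1 coding and the product term, each main-effect SE is 0.0894, identical to 250 v 250. With factors coded −1/2 and +1/2, or with no product term, it is 0.0632, identical to 500 v 500. No coding gives the 250 v 500 value. The interaction SE is √(4/250) = 0.1265, so its MDE is 2.80 × 0.1265 = 0.354 SD (6.1 and 4.2 mmHg).

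**Severe hypertension, 10.2% v 4.39%.**

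| Contrast | Continuity-corrected z | Wald (log-odds) | Pooled z |
|---|---|---|---|
| 250 v 500 | 80.4% | 85.1% | 84.1% |
| 250 v 250 | 64.4% | 68.1% | 70.7% |

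The plan names no binary method; the continuity-corrected one comes closest to its 80%. At 250 v 250 the RR detectable with 80% power is 0.342 (corrected), 0.350 (Wald) or 0.374 (pooled), against the stated 0.43.

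For the margin, the effect-coded logistic coefficient is the mean of the two log-odds ratios, with SE = ½√Σ[1/(n p(1−p))] over four cells of 250.

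- Other intervention has no effect: the log-odds ratio is 0.907 in both strata and the SE is 0.264. Then 0.907/0.264 − 1.96 ≈ 1.48, so power is 93%. Detectable RR 0.53.
- Both work at RR 0.43, multiplicatively (cells 10.2%, 4.39%, 4.39%, 1.89%): the mean log-odds ratio is 0.888 and the SE is 0.336. Then 0.888/0.336 − 1.96 ≈ 0.69, so power is about 75% (77% by simulation). Detectable RR about 0.40.

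**Post hoc 2-df test at 0.22 SD.** 88% power if the effect is additive, 59% if it is present only when the intervention is given alone.

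**Readings needed.** At 250 v 250 coding, 80% power at 0.22 SD needs 325.3 readings per cell, or 1301 in all. That is 93% of the 1404 in Table 5. N=1000 is 1000/1404 = 71%.

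**Aim 2, separately.** Noncentral F, 3 df, 8 cells: f = 0.192 at N=300, matching the stated 0.19. The planned race-by-intervention test uses N=1000, where f = 0.105.

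**The case against.** The strongest reply is that this is a disclosed planning approximation with a stated reason, and that its 80% is correct for the groups it names. That is fair as far as the arithmetic goes. But the reason given does not lead to 250 v 500: a two-group calculation in mmHg is just as readable at 250 v 250 or 500 v 500.

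Second, the blood pressure shortfall is modest. At the rounded targets, 250 v 250 gives 74% for systolic and 80% for diastolic pressure. With all 1053 retained in Table 5 (about 263 per cell), the figures are 71% at 0.22 SD, 76% and 82%. This stands. The material shortfall is in severe hypertension.

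Third, the text on main effects points fairly clearly to 250 v 250, and the margin rests on one opening phrase. This also largely stands. It makes 250 v 250 the natural default, and on that reading the stated power is too high.

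Fourth, the plan notes: "The power consideration does not consider adjusting covariates and thus is conservative". Adjustment could help for blood pressure. Restoring 80% at 250 v 250 needs (0.22/0.251)² = 1 − R², so R² of about 0.23 at 0.22 SD, or about 0.14 at 4 mmHg. The documents give no R².

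The 2-df test is not a rescue: it is post hoc, optional, not what was powered, and its power lies on either side of 80% depending on the interaction.

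**Conclusion.** The concern holds. The stated 80% is right for 250 v 500 and wrong for either contrast the plan could mean. Under the model as described, power at 0.22 SD is 69%. The blood pressure MDEs rise only slightly, to 4.3 and 3.0 mmHg, but power for severe hypertension at the stated reduction falls to 64–71%. On the margin, blood pressure power is well above 80%, while severe hypertension runs from 93% down to about 75% depending on whether the other intervention works.

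These figures assume two-sided 0.05 for each test, with no allowance for several co-primary outcomes or two factors, and equal cells of 250. The blood pressure figures further assume 1000 in-office readings at 7–10 days. N=1000 is a 6-week retention figure, and no expected 7–10 day attendance is given. The 75% figure assumes both interventions act at RR 0.43 multiplicatively, which the plan does not state.

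The Aim 2 mismatch is minor: it understates power and harms no conclusion.

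**What to change.** In 'Aim 1 Analytic Approach', name the primary contrast for each factor and the coding that produces it. Then restate the power section and Table 6 for that contrast.

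1. **If the 0/1 interaction model stays primary:** state 80% power for 0.251 SD (4.3 mmHg systolic, 3.0 mmHg diastolic) and for an RR of about 0.34–0.37, naming the binary method. This changes wording and figures only. The cost is a less favourable statement.
2. **If the factorial margin is made primary:** code the factors −1/2 and +1/2, keep the product, and state 0.177 SD (3.1 and 2.1 mmHg). For severe hypertension, give the RR detectable by the fitted logistic coefficient: about 0.53 if the other intervention has no effect, about 0.40 if both work as above. Report the interaction (MDE 0.354 SD) and the single-cell contrasts beside it, because Aim 1 also asks about the combination. This changes what the main effects mean, so the interpretation text must be rewritten too, before any outcome data are examined by arm.

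Under either option, say that the blood pressure figures assume 1000 in-office readings, about 71% of the roughly 1404 enrolled. If credit is taken for covariate adjustment, state the assumed R². Separately, restate Aim 2 as f of about 0.105 at N=1000. Neither option needs more patients.
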